### 6.2.2 Angiographic Exclusion Criteria

1. Unprotected left main coronary artery disease (obstruction  $>50\%$  in the left main coronary artery that is not protected by  $\geq 1$  non-obstructed bypass graft to the left anterior descending (LAD) or left circumflex (LCX) artery or a branch thereof.

2. Target vessel exhibiting multiple lesions with >60% diameter stenosis outside of a range of 5 mm proximal and distal to the target lesion based on visual estimate or on-line quantitative coronary angiography (QCA).
3. Target lesion exhibiting an intraluminal thrombus (occupying >50% of the true lumen diameter) at any time prior to the start of the intervention.
4. Lesion location that is aorto-ostial or within 5 mm of the origin of the LAD or LCX.
5. Target lesion with side branches >2.0 mm in diameter.
6. Target lesion involving a bifurcation (either stenosis of both main vessel and major branch or stenosis of just major branch).
7. Target lesion with severe calcification.
8. Target vessel exhibiting excessive tortuosity that may impede stent delivery and deployment at target lesion.
9. Target lesion that is located in a native vessel distal to an anastomosis with a saphenous vein graft or a left/right internal mammary artery (LIMA/RIMA) bypass.

## 7 Treatment Methodology

**Table 2: Summary of Study Procedures from Screening through End of Follow-Up**

Study Requirement	Screening		Procedure	Post-Procedure					
	Within 7 Days Prior to Procedure	24 Hours Prior to Procedure		Hospital Discharge	30 Days ( $\pm 2$ Weeks)	9 Months ( $\pm 1$ Month)	1 Year ( $\pm 1$ Month)	2 Years ( $\pm 1$ Month)	3 Years ( $\pm 1$ Month)
Informed consent	X								
Medical history	X								
Clinical assessment and physical exam	X			X					X(7)
Telephone assessment					X	X	X	X	X
CBC w/differential (1)	X								
Serum creatinine	X								
INR, APTT	X								X(7)
Pregnancy test	X(2)								
CK/CK-MB/troponin		X(3)		X(6)					X(7)
12-lead ECG		X(4)							X(7)
Record of relevant medications (5)		X		X	X	X	X	X	X
Coronary angiography			X						
Stenting			X						
Record of adverse events			X	X	X	X	X	X	X

APTT: activated partial thromboplastin time; CBC: complete blood count; CK: creatinine kinase; CK-MB: creatinine kinase myocardial band; ECG: electrocardiogram; INR: international normalized ratio

- (1) Collection of CBC differentials during the index hospitalization should be done as per the respective institutions standard of care. However, if the white blood count (WBC) is abnormal, it is recommended to perform the CBC differential before and after the procedure.
- (2) For females of childbearing potential.
- (3) Pre-procedure cardiac enzymes: CK, CK-MB or troponin performed within 24 hours prior to the procedure may be used as the baseline cardiac enzymes provided there have been no signs or symptoms of myocardial ischemia between the time of cardiac enzymes test and the time of arterial access.
- (4) Pre-procedure 12-lead ECG: an ECG performed within 7 days prior to the procedure may be used as the baseline ECG provided there have been no signs or symptoms of myocardial ischemia between the time of ECG and the time of arterial access.
- (5) Relevant medications: statins, angiotensin converting enzyme inhibitors (ACE-I), angiotensin receptor blockers (ARB), beta-blockers and anti-platelets.

- (6) CK and CK-MB will be measured at 6- 8 hours post procedure, 12-16 hours post procedure and 20-24 hours post procedure (or upon discharge, whichever comes first). If any CK elevation (CK above ULN) is noted post procedure, CK and CK-MB measurements will continue to be performed every 8 hours for 24 hours starting from when the first elevation is noted and recorded on the appropriate eCRF. If total CK values are within normal ranges, CK-MB measurements may not be performed (per hospital standards). However, it is strongly encouraged that CK-MB measurements are obtained with every total CK drawn, even if CK values are within normal limits. It is also recommended that sites collect CK and CK-MB preferentially over troponin in the peri-procedural period subsequent to the index procedure. In the case where CK and CK-MB are not available, troponin can be used.
- (7) These assessments and tests will be performed only if clinically warranted.

## 7.1 Subject Screening/Assessment

Signed written informed consent must be obtained for all subjects who are potential study candidates prior to enrollment. Additionally, the following evaluations must be completed for all subjects unless otherwise specified:

*Within 7 Days of Enrollment:*

- Medical history.
- Clinical assessment and physical examination.
- Complete blood count (CBC) with differential (if possible as per the respective institutions standard of care).
- Chemistry screen including serum creatinine.
- Coagulation including international normalized ratio (INR), activated partial thromboplastin time (APTT). Note: must be checked prior to heparin therapy.
- Pregnancy test (for females of childbearing potential).

*Within 24 hours of Enrollment:*

- CK, CK-MB or troponin levels.
- 12-lead ECG (an ECG performed within 7 days prior to the procedure may be used as the baseline ECG provided there have been no signs or symptoms of myocardial ischemia between the time of ECG and the time of arterial access). A copy of the ECG trace should be sent to the ECG core laboratory.
- Record of relevant medications.

## 7.2 Procedural Information

For information describing the procedural steps and materials necessary for appropriate use of the NIRxcell Stent System, refer to the US Instructions for Use.

Additionally, note the following:

- *Start of the Procedure and Enrollment*

The start of the procedure is defined as the time of arterial cannulation. Actual enrollment in the study occurs at the time the study device is introduced into the body. If the angiogram performed at the index procedure indicates that the subject is not a candidate for the study, this subject is not considered enrolled.

- *Angiographic Protocol Requirement*

- Following intracoronary injection of 50–200 µg nitroglycerin (NTG), obtain baseline angiograms using at least  $\geq 2$  near orthogonal views, best demonstrating the coronary artery stenosis, as specified in the angiographic protocol.
- Before stent placement, obtain a single working view of the coronary artery stenosis, as specified in the angiographic protocol.

- *Pre-Dilatation*

If the target lesion fulfills eligibility criteria, the target lesion must be pre-treated with standard percutaneous transluminal balloon angioplasty. This clinical protocol does not allow for direct stenting of the target vessel.

Attention must be paid to the pre-dilatation technique to avoid balloon injury to any segment of the vessel that will not be entirely covered by the stent ('geographical miss').

Pre-dilatation must be performed using a balloon with the following 3 characteristics:

1. A diameter  $\geq 0.5$  mm smaller than the treatment stent.
2. A length matching or shorter than the lesion length to be dilated (to avoid dilatation of the vessel wall adjacent to the stent).
3. A length shorter than the stent to be implanted.

The use of other therapy (e.g. cutting balloons, atherectomy, laser, thrombectomy, etc.) is not allowed.

- *Selection of Appropriately Sized Stent*

Select an appropriately sized stent based on angiographic vessel measurements (approximately 2–4 mm longer than the measured shoulder-to-shoulder lesion length, with a stent to distal reference vessel ratio of 1:1 or 1.1:1.0). The intention should be to cover the whole lesion with 1 stent of adequate length.

**Note:** Additional NIRxcell Stent Systems should be used, at the physician's discretion, for sub-optimal result, or in the event of bailout procedures, as defined below.

- *Bailout Procedures*

The intention should be to cover the index lesion with 1 stent of adequate length. Bailout procedures and additional stenting for sub-optimal results should be avoided unless required for subject safety. If a subject enrolled in the study experiences a major dissection or an occlusive complication (as evidenced by decreased target vessel flow, chest pain, or ischemic ECG changes that do not respond to repeat balloon inflations, NTG, intracoronary verapamil, intracoronary diltiazem, or lytic agents), bailout procedures may be performed. For bailout procedures or in the event of a sub-optimal result, further stenting may be employed, at investigator's discretion, using the NIRxcell Stent Systems, as required.

- *End of the Procedure*

The end of the procedure is defined as the time that the final guiding catheter is withdrawn from the subject. Closure of the arterial puncture site will be performed as per laboratory

standards. The hemostasis introducer sheath(s) may be removed when the subject's activated clotting time (ACT) is <150 seconds or per the physician's discretion. If a guide catheter is introduced once the procedure is considered over, as defined above, or the subject is returned to the procedure room and interventional therapy is performed, this should be considered a repeat intervention.

- *Adverse Events Recording*

All adverse events (AEs) occurring following informed consent signature must be recorded.

**Note:** Bailout procedures performed during the same catheterization as the index stenting procedure shall be considered part of the index procedure.

### **7.3 Post-Procedure Assessment (Hospital Discharge)**

Clinical assessment of a subject's condition must be performed according to the details below. The research coordinator will review the follow-up requirements with the subject to help ensure compliance with the follow-up schedule. Telephone numbers must be obtained from the subject to ensure the ability to contact him/her. These phone numbers should include all home numbers, work numbers and primary physician numbers. A phone number of a relative or friend should also be requested.

#### **The following assessments will be performed at hospital discharge:**

- Clinical assessment and physical examination.
- CK and CK-MB will be measured at 6- 8 hours post procedure, 12-16 hours post procedure and 20-24 hours post procedure (or upon discharge, whichever comes first). If any CK elevation (CK above ULN) is noted post procedure, CK and CK-MB measurements will continue to be performed every 8 hours for 24 hours starting from when the first elevation is noted and recorded on the appropriate eCRF. If total CK values are within normal ranges, CK-MB measurements may not be performed (per hospital standards). However, it is strongly encouraged that CK-MB measurements are obtained with every total CK drawn, even if CK values are within normal limits. It is also recommended that sites collect CK and CK-MB preferentially over troponin in the peri-procedural period subsequent to the index procedure. In the case where CK and CK-MB are not available, troponin can be used. Record of relevant medications (statins, angiotensin converting enzyme inhibitors [ACE-I], angiotensin receptor blockers [ARB], beta-blockers and anti-platelets).
- Record of all AEs that occurred since the end of the index procedure.

## 8 Concomitant Medications

Concomitant medications to be used before, during and after the stenting procedure are as follows:

**Table 3: Summary of Concomitant Medications Regimen**

	Pre-Procedure	Procedure	Post-Procedure
Aspirin	A minimum of 150 mg (within 24 hours prior to procedure).	---	75–100 mg daily indefinitely.
Clopidogrel or Prasugrel/ Ticagrelor	Loading dose of 600 mg clopidogrel within 24 hours prior to index procedure or immediately post-procedure (within 30 minutes). Alternatively, loading dose of 60 mg prasugrel or 180 mg ticagrelor. No loading dose is required for subjects on chronic thienopyridine therapy.	---	Post-procedure treatment with the same thienopyridine agent for a minimum of 1 month as follows: Clopidogrel: 75 mg daily. Prasugrel: 10 mg daily; a lower dose of 5 mg daily is allowed for subjects <60 kg. Ticagrelor: 90 mg twice daily.
Heparin or Bivalirudin	---	Per routine hospital practice. For heparin, a bolus of 50–80 units/kg is recommended. If heparin is administered, it is recommended to maintain ACT of $\geq$ 250 seconds (or $\geq$ 200 seconds if a glycoprotein IIb/IIIa receptor blocker is administered) throughout the interventional portion of the procedure.	---
Glycoprotein IIb/IIIa Inhibitor	---	Per investigator's discretion.	---
Intracoronary Nitroglycerin or Intracoronary Isosorbide or Dinitrate	---	To eliminate coronary artery spasm that would interfere with accurate measurement of lumen obstruction due to plaque alone, 100–200 $\mu$ g nitroglycerin or 1–3 mg of isosorbide or dinitrate must be administered prior to baseline and post-intervention angiograms.	---

## **9 Follow-Up Assessments**

Follow-up will be conducted at 30 days, 9 months, and 1, 2, and 3 years post-procedure via telephone call. Refer to the text below for details.

Additional unscheduled follow up visits/phone calls may occur as clinically warranted.

The window for the 30-day follow-up contact will be  $\pm 2$  weeks. For the 1-, 2- and 3-year contacts, the window will be  $\pm 1$  month.

### **9.1 30-Day ( $\pm 2$ Weeks) Contact**

- Record of relevant medications.
- Record of all AEs that occurred since last subject contact.

### **9.2 9-Month ( $\pm 1$ Month) Contact**

- Record of relevant medications.
- Record of all AEs that occurred since last subject contact.

### **9.3 1-Year ( $\pm 1$ Month) Contact**

- Record of relevant medications.
- Record of all AEs that occurred since last subject contact.

### **9.4 2-Year ( $\pm 1$ Month) Contact**

- Record of relevant medications.
- Record of all AEs that occurred since last subject contact.

### **9.5 3-Years ( $\pm 1$ Month) Contact**

- Record of relevant medications.
- Record of all AEs that occurred since last subject contact.

### **9.6 Unscheduled visit/Phone follow up**

- Record of relevant medications.
- Record of all AEs that occurred since last subject contact.
- Additional assessments and tests may be performed if clinically warranted.

During each specified evaluation, the corresponding electronic case report form (eCRF) must be completed per the written instructions provided by the sponsor. Although not anticipated, should the appropriate authorized regulatory bodies request additional follow-up, the physicians and subjects will be requested to adhere accordingly.

### **Detailed Explanations**

**Adverse Events:** Adverse events occurring (1) from time of index procedure to 30 days follow-up contact, (2) From 30 days follow up contact to 1 year follow-up contact, (3) From 1 year follow-up contact to 2 years follow-up contact, and (4) From 2 years follow-up contact to 3 years follow-up contact, will be recorded. In the event of an AE that is associated with repeat

angiography/revascularization, the event related coronary angiograms and catheterization report must be captured and submitted to the data center within 10 working days of knowledge of the event. Angiographic data collected during any repeat procedure on the target vessel must be made available to the CEC for an independent review and assessment. Likewise, the angiographic images should be submitted to the core laboratory for an independent review and assessment of the target lesion and study stent.

**12-Lead ECG:** According to each site's standard of care.

**CBC With Differential:** Hematology testing due to anti-platelet therapy should follow the routine standard of care.

**CK, CK-MB and Troponin:** CK, CK-MB or troponin will be obtained pre-procedure (within 24 hours of the index procedure). Post procedure, CK and CK-MB will be measured at 6- 8 hours, 12-16 hours and 20-24 hours post procedure (or upon discharge, whichever comes first). If any CK elevation (CK above ULN) is noted post procedure, CK and CK-MB measurements will continue to be performed every 8 hours for 24 hours starting from when the first elevation is noted and recorded on the appropriate eCRF. If total CK values are within normal ranges, CK-MB measurements may not be performed (per hospital standards). However, it is strongly encouraged that CK-MB measurements are obtained with every total CK drawn, even if CK values are within normal limits. It is also recommended that sites collect CK and CK-MB preferentially over troponin in the peri-procedural period subsequent to the index procedure. In the case where CK and CK-MB are not available, troponin can be used.

**Relevant Medications:** Statins, ACE-I, ARB, beta-blockers and anti-platelets.

**10 Total Expected Duration of the Clinical Investigation**

- The clinical investigation is estimated to commence in June 2015.
- The enrollment is estimated to commence in July 2015.
- Enrollment completion is estimated for October 2016.
- The last patient follow up at 3 years is estimated for October 2019.
- Total expected duration of the clinical investigation is approximately 4-5 years.

## 11 Adverse Events

In this study, subjects should be encouraged to report adverse events (AEs) spontaneously or in response to general, non-directed questioning (e.g. "How has your health been since the last contact?"). Any time during the study, the subject may volunteer information that resembles an AE. If it is determined that an AE has occurred, the Investigator should obtain all the information required to complete the AE eCRF.

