## 12.2 Performance Goal

The goal of the primary analysis will be to assess the comparability of the observed primary endpoint rate for the study stent to the meta-analysis derived rate (23.2%). Based upon the meta-analysis, the expectation for the true primary endpoint rate for the study stent is equal to 23.2%. However, since strict equality cannot be assessed statistically, this non-randomized, single-arm study will assess if the study stent 3-year TVF rate falls significantly below 34.8%. Specifically, this study will assess the ability of the study stent to meet a performance goal of 34.8%, which is a 50% increase over the expected rate of 23.2% obtained from the meta-analysis.

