## 12.3 Primary Endpoint and Sample Size Calculation

The null hypothesis for this study states that the NIRxcell will have a primary endpoint rate greater than or equal to 34.8%. The alternative hypothesis states that the NIRxcell will have a primary endpoint rate less than 34.8%.

Specifically:

$$H_0: \pi_{\text{NIRTRAKS}} \geq 34.8\%$$

$$H_A: \pi_{\text{NIRTRAKS}} < 34.8\%$$

where  $\pi_{\text{NIRTRAKS}}$  is the true primary endpoint rate for the study stent and the 34.8% is the meta-analytically derived performance goal (PG) for the primary endpoint rate. Rejection of the null hypothesis will signify that the performance goal has been met, and that the study stent's primary endpoint rate is less than 34.8%.

The primary hypothesis test will be carried out by comparing the upper bound of the exact 1-sided 95% confidence interval of the 3-year TVF rate to 34.8%, the PG. If this upper bound is less than 34.8%, then it will be considered that the study stent meets the performance goal. The necessary sample size for testing the primary hypothesis was estimated with PASS software using exact hypothesis testing based on the exact distribution with the following assumptions:

- Type I error ( $\alpha$ ) = 0.05 (1-sided).
- Statistical power ( $1 - \beta$ ) = 83%.
- PG = 34.8%.
- $\pi_{\text{NIRTRAKS}} = 23.2\%$ .

An evaluable sample size of 105 provides 83% power to reject the above null hypothesis in favor of the alternative. Thus, 131 subjects will be enrolled to account for loss to follow-up, which is expected to be approximately 7.0% per year.

The loss to follow-up in previously published stent trials with long-term follow-up is low. In the SIRIUS trial, complete data compliance for all 5-year follow-up end points was 93.6% and 94% in the intervention and control groups, respectively. At 9 months the clinical compliance was 100% in both groups. In the ENDEAVOR II trial, out of 1,197 enrolled subjects, 1,167 were followed for 4 years (97.4%). In the RAVEL trial, complete data sets were available for 94.2% of subjects randomly assigned to sirolimus-eluting stents and for

94.1% of subjects randomized to BMS. In the TAXUS IV trial, out of 1,314 intention-to-treat (ITT) subjects, 5-year data were available for 1,294 (98.4%) subjects. In view of these data, we believe a yearly 7% loss-to-follow-up estimate is conservative and encompasses wide margins of safety.

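### Post-discharge TVF events are detected mainly by telephone calls, a year apart after year 1, using a general non-directed question, so unreported MIs and revascularizations count as event-free and lower the rate

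*Protocol*

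**What the plan says.** Protocol section 9 states: "Follow-up will be conducted at 30 days, 9 months, and 1, 2, and 3 years post-procedure via telephone call". SAP section 2.2.6 repeats that schedule. Sections 9.1 to 9.5 list the same two items for each contact: relevant medications, and "Record of all AEs that occurred since last subject contact". The only stated way of eliciting adverse events is in section 11, where "subjects should be encouraged to report adverse events (AEs) spontaneously or in response to general, non-directed questioning"; the example given is an open question about the subject's health since the last contact.

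Under Table 2 of the protocol, ECG and cardiac biomarkers during follow-up are done only if clinically warranted. A missed contact is carried to the next scheduled one (section 5.2).

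The later steps depend on an event being known:
- The CEC adjudicates endpoint events and investigator-reported adverse events that could be endpoints (section 5.1).
- Source documents are sent when an endpoint event is suspected or identified (section 11.5).
- Repeat angiograms go to the CEC and core laboratory when an adverse event involves repeat angiography (section 9, Detailed Explanations).

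**The concern.** An open question suits unsolicited adverse events. It is a weak way to ascertain a predefined composite endpoint over a long recall period. A subject who had a stent placed at another hospital eight months ago and now feels well can truthfully answer that all is well.

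If that subject completes the 3-year call, the outcome is not recorded as missing. The subject enters the denominator as event-free in the exact binomial analysis and is carried to 3 years without an event in the Kaplan-Meier analysis. Neither censoring nor the multiple imputation in protocol section 12.8 can correct this. There is no concurrent arm to share the loss, so this source of error moves TVF in one direction, in favour of the device.

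**Working it through.** **1. The plan's own figures reproduce.** Section 12.3 states: "An evaluable sample size of 105 provides 83% power to reject the above null hypothesis in favor of the alternative".
- Inputs: one-sided alpha 0.05, performance goal 34.8%, expected TVF 23.2%, exact binomial test.
- The largest c with P(X ≤ c | 105, 0.348) ≤ 0.05 is c = 28, with exact alpha 0.0476.
- Power is P(X ≤ 28 | 105, 0.232) = 0.831, against 83% stated.
- Loss at 7% per year gives 0.93³ = 0.8044. Then 105/0.8044 = 130.5, so 131 enrolled, as stated.
- SAP section 4.1: 65 × 0.8044 = 52.3, against about 52 stated.

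**2. Recall period.** Contacts at years 1, 2 and 3 are nominally 12 months apart. With windows of ±1 month the gap can reach 25 − 11 = 14 months. If the 2-year contact is missed it can reach 37 − 11 = 26 months.

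**3. Effect of one missed event under the current SAP.** SAP section 4.3.2 reports the rate with an exact two-sided 95% CI. With n = 52, one event is 1/52 = 1.9 points. The limits are the 0.025 quantile of Beta(x, n − x + 1) and the 0.975 quantile of Beta(x + 1, n − x).

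| Events recorded | Rate | 95% CI |
|---|---|---|
| 12/52 | 23.1% | 12.5% to 36.8% |
| 11/52 | 21.2% | 11.1% to 34.7% |
| 10/52 | 19.2% | 9.6% to 32.5% |

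Twelve events are used because 52 × 0.232 = 12.1.

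**4. Range under assumed miss rates.** Let m be the share of subjects with TVF whose event is never reported. The documents give no m, so the values below are assumptions. Recorded rate = 0.232 × (1 − m). Expected missed events = 52 × 0.232 × m. The last column is the chance that the whole two-sided interval lies below the true 23.2%.

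| m | Recorded rate | Bias (points) | Missed events of 52 | Interval wholly below truth |
|---|---|---|---|---|
| 0 | 23.2% | 0 | 0 | 1.0% |
| 5% | 22.0% | −1.2 | 0.6 | 1.7% |
| 10% | 20.9% | −2.3 | 1.2 | 2.6% |
| 20% | 18.6% | −4.6 | 2.4 | 6.2% |

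**5. A milder case.** Section 12.1 assumes that half of TVF events occur in the first year, when contacts are closer together. If only the later half is exposed, the recorded rate is 0.232 × (1 − 0.5m): 22.6%, 22.0% and 20.9% for m = 5%, 10% and 20%. The bias is halved.

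**The case against.** **Other sources of detection exist.** Section 13.3 bases primary data collection on hospital chart review by site coordinators, and monitors check data against source. Peri-procedural MI is found by serial in-hospital CK and CK-MB (section 7.3). The CEC rules on all deaths (section 12.12), and deaths of unknown cause count as cardiac (section 4.2.3). This stands. It would be wrong to say that the telephone question is the only source, or that the whole composite is exposed. But section 13.3 does not tie chart review to each contact or to other hospitals, and SAP Table 15 lists visit data taken from medical records alone as a compliance violation. The remaining gap is post-discharge MI and revascularization, especially outside the study site.

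**The eCRF may contain prompts.** The forms, their completion guidelines and the CEC charter are not part of the documents. In addition, the SAP cites protocol version 3.0, while the protocol text here is version 1.2. Directed questions may exist. Even so, the only elicitation method the protocol states is the non-directed one.

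**Telephone follow-up was deliberate.** Section 12.1 explains that mandatory angiography inflates revascularization. That argument concerns imaging. Asking whether a procedure took place does not cause one.

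**The net bias is not shown.** Counting unknown deaths as cardiac, and keeping early events in the denominator while dropping event-free withdrawals, both push TVF up. This is fair. Only the direction of this one component is established.

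**A tempting stronger reading.** A reader might infer that one missed event carries the study across the 34.8% goal, since the two-sided upper limit falls from 36.8% at 12/52 to 34.7% at 11/52. The documents do not support this. Section 12.3 compares the "upper bound of the exact 1-sided 95% confidence interval of the 3-year TVF rate to 34.8" percent, and on that one-sided bound 12/52 already gives 34.69%. The design with 52 evaluable subjects belongs to the SAP, which is descriptive and performs no test.

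**Conclusion.** The concern holds for post-discharge MI and revascularization. The stated method can miss events that are not volunteered, the downstream safeguards do not look for them, and each such event in a subject with 3-year follow-up lowers the reported rate. The effect is 1.9 points per missed event at 52 evaluable subjects. At a true rate of 23.2% it is roughly 1 to 5 points if 5% to 20% of events were missed, or half that if only events after year 1 are exposed. Those miss rates are assumptions, and the actual rate cannot be derived from the documents.

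The consequence is a descriptive TVF rate and interval that may be too low. It does not amount to a false pass against a performance goal. The weakness is worth correcting because the remedy is cheap, and it does not invalidate the study. If the eCRF already carries directed endpoint questions, what remains is to state them in the protocol.

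**What to change.** In protocol sections 9 and 11, keep the open question and add a short scripted set at every contact. It should ask about any hospital or emergency visit, heart attack, repeat coronary angiogram, PCI or bypass since the last contact, with date and hospital. A yes to any item should trigger collection of source records for the CEC, including records from other hospitals. When the subject is not reached, put the same questions to the relative, friend or primary physician whose numbers are already collected under section 7.3.

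The cost is a few minutes per call and one eCRF page. No visit, test or change in sample size is needed. If calls have already been completed, the study report should say what was asked at each contact and which records were checked.
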